## 10.0 STUDY METHODS

### Trial design

A single-blinded, placebo controlled, randomized clinical trial, with nested immunological studies. Participants are randomized 1:1:1:1 to four groups: BCG 14 days before, together with, or 14 days after IIV compared to placebo.

People  $\geq 65$  years of age who plan to accept the offer of seasonal influenza vaccination are eligible for participation.

Participants are vaccinated once at day 0 and twice at day 14 (one shot in each arm). All participants receive the standard seasonal IIV recommended by the Danish Board of Health. The participants will come back for a follow-up interview at day 42 and all are followed for six months post-randomization with electronic questionnaires about their health. These include information on symptoms and disease, potential side effects, other vaccinations, visits to general practitioner or on call doctor, and hospitalizations. Every survey period is 14 days, starting from day 0 (inclusion).

Blood samples for influenza antibody testing are collected from all participants at day 14 and 42. Samples for further immunological analyses are collected from subgroups at day 0, day 14, day 21, and day 42.

Vaccination schedule:

Group	Day 0 (one shot)	Day 14 (two shots)	Day 42
1	BCG	IIV + Placebo	Follow up visit
2 (Control)	Placebo	IIV + Placebo	Follow up visit
3	Placebo	IIV + BCG	Follow up visit
4	IIV	Placebo + BCG	Follow up visit

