### **Secondary outcomes**

*Self-reported infections:*

Infections are identified through information given by the participants in the electronic follow-up questionnaires, where they are asked to describe disease episodes every 14 days. They are asked if they have been ill, and then asked to cross off their symptoms on a list. Furthermore, we ask them to provide the most likely cause for their illness. Disease episodes are characterized as infections if participants report symptoms compatible with an infectious disease or they report an infectious disease diagnose as the cause of their illness. Criteria for self-reported infection:

- Having one or more of the following symptoms: fever, cough, sore throat, runny nose/nasal congestion (common cold symptoms), loss of smell or taste sense, vomiting, or diarrhea with or without general symptoms such as headache, myalgia, dysarthria, or fatigue.
- Having dyspnea AND fever with or without general symptoms such as headache, myalgia, dysarthria, or fatigue.
- Having described an infectious disease as the self-estimated cause of illness. This is a free-text field and participants answers will be classified as infectious disease or not by medically trained study personnel.

Baseline for analysis is set at day 14 reflecting completion of the allocated vaccinations. We will however also conduct the analysis from day 0-14. Participants can register a maximum of one infectious disease event per survey period (14 days).

A secondary analysis of association between influenza antibody level and subsequent risk of infection will be performed to test if high antibody titers correlate with risk of infection.

*Immunological outcomes (subgroup analyses):*

A random subset of participants (the first to accept) have extra blood samples taken for further immunological analyses.

1. Lymphocyte-dependent responses 7 days after influenza vaccination
2. The induction of innate immune memory 14- and 42-days post-randomization

For the lymphocyte analyses, 10 participants from groups 1-3 will have blood drawn on day 21, exactly 7 days after influenza vaccination. We will assess the effect of the different treatment combinations on the response to the influenza vaccine, examining activated

influenza antibody-secreting B-lymphocytes. Due to the different timing of the influenza vaccination, participants from group 4 are not part of this analysis.

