For the trained immunity analyses, 15 participants from each group will have extra blood samples taken on day 0, 14, and 42. Peripheral blood mononuclear cells (PBMCs) are isolated from the samples and subsequently stimulated in vitro with various antigens. The immune function will be assessed by cytokine production capacity measured by Luminex technology after stimulation. The outcome measure for this analysis is concentration of different types of cytokines produced following stimulations. We will compare fold change in cytokine production between the groups at the various timepoints with and without adjustment for responses in control medium. This will allow us to determine whether BCG in the different combinations with influenza vaccine induces trained immunity in this population.

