**List of variables:**

Variable name	Definition	Type	Scale
Primary outcome: Change in antibody levels to influenza virus strains included in the IIV, comparing levels at day 14 and day 42.			
ab_diff_strain	Influenza antibody titer (GMT) day 42 minus day 14. For each strain.	Continuous	<20 to 320
seroconv	Seroconverted after influenza vaccination (4-fold increase in Ab titer). For each strain.	Binary	0: no 1: yes
Secondary outcome, self-reported infections:			
infection	Infection or symptoms consistent with infection (0 or 1 every survey period).	Binary	0: no 1: yes
Secondary exposure:			
ab_day42_cat	Influenza ab titer day 42 (GMT). Secondary exposure.	Categorical	1. quartile 2. quartile 3. quartile 4. quartile
Secondary outcome, immunological:			
b_lymph	Number of activated B-cells. For all relevant subtypes.	Continuous	0.0-0.3 x 10  /L

cytokine_stim_day	Cytokine concentration (TNF $\alpha$ , IL-1 $\beta$ , IFN- $\gamma$ ) after stimulation with: Poly(I:C), Pam3CSK4, LPS, and influenza vaccine at the various timepoints (day 0, 14, and 42).	Continuous	0-1500 pg/mL
diff_cytokine_stim_day	Fold change in cytokine concentration from baseline value (day 0) to day 14 and 42 after stimulation with various stimuli. Compared between the randomization groups. Using randomization group as exposure (categorical).	Continuous	0-10

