#### Secondary outcomes:

##### *Self-reported infections:*

The hazard ratio of infections will be estimated using an Andersen-Gill Cox proportional hazards regression model with infections included as recurrent events and time since inclusion as underlying time scale. The proportional hazards assumption will be tested using Schoenfeld residuals. As participants are only able to report one infectious episode during a follow-up questionnaire, the event will be assigned to the first day within the questionnaire period, and the following 14 days of follow-up excluded for analyses as it represents risk free time.

Association between influenza antibody titer level at day 42 and rate of infections will also be explored in Andersen-Gill Cox proportional hazards regression model, using antibody titer at day 42 as exposure and self-reported infections after day 42 as outcome. Antibody titers will be categorized into quartiles or similar relevant categories. The analysis will be adjusted for sex and age group.

Absolute risk reduction will be calculated using Cox regression.

*Immunological outcomes (subgroup analyses):*

Mean change in number of activated B-cells, concentration of cytokines, as well as fold change in cytokine concentration after stimulation from day 0 to day 14 and from day 14 to day 42 will be compared between the control group and the three treatment groups in linear regression analyses. With and without adjustment for responses in the control condition.

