### Figure 3: Results trained immunity.

Boxplots showing fold increase in cytokine production after stimulation with bacterial antigens and influenza vaccine at day 0, day 14, and day 42 for each treatment group.

\* Denotes within-group statistically significant change in cytokine levels between day 0 and 14 or between day 14 and 42

Δ Denotes between group statistically significant different change in cytokine levels between day 0 and 14 or between day 14 and 42

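### Part B takes the day-42 cytokine fold change from day 0 in the variable list but from day 14 in the analysis, so a BCG effect still present at day 42 in Group 1 has no fold-change test

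*SAP*

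**What the plan says.** All references are to Part B of the SAP.

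- **Section 13.0, list of variables.** The fold-change variable is defined as "Fold change in cytokine concentration from baseline value (day 0) to day 14 and 42 after stimulation with various stimuli". Day 0 is the reference for both later samples.
- **Section 14.0, immunological outcomes.** The fold change is analysed over two consecutive intervals, "from day 0 to day 14 and from day 14 to day 42 will be compared between the control group" and the three treatment groups, by linear regression. No day 0-42 interval is named.
- **Section 15.0, Figure 3.** The between-group symbol "Denotes between group statistically significant different change in cytokine levels between day 0 and 14 or between day 14 and 42". The within-group symbol uses the same two intervals. The figure plots fold increase at all three days and does not state the reference for the plotted values.
- **Section 13.0, secondary outcomes.** The target is "The induction of innate immune memory 14- and 42-days post-randomization". The text adds: "We will compare fold change in cytokine production between the groups at the various timepoints with and without adjustment for responses in control medium". Neither sentence names a reference day.
- **Section 10.0, trial design.** The arms are "BCG 14 days before, together with, or 14 days after IIV compared to placebo". In the schedule table Group 1 receives BCG on day 0, and Groups 3 and 4 receive it on day 14. Group 4 receives the influenza vaccine (IIV) on day 0, and the other groups receive it on day 14.
- **Sampling (section 13.0).** "15 participants from each group will have extra blood samples taken on day 0, 14, and 42".

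**The concern.** The day-42 fold change has two reference days, and the choice between them changes the question in the BCG-first arm. Group 1's day-14 sample is taken two weeks after BCG, so any effect established by then is already in the denominator of the day 14-42 fold change. That contrast asks whether the effect grew or faded after day 14. It does not ask whether an effect is present at day 42, which is one of the two times at which the plan says it will assess innate immune memory.

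Two things are at stake. The planned fold-change analysis has no test of the BCG effect at day 42 in Group 1. And with two definitions in the document, the choice between them could be made after the results are known.

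**Working it through.** The plan gives no effect size, standard deviation or power for the cytokine outcome, so there is no figure to reproduce. The check uses an identity and illustrative values.

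**1. Identity.** Let FC(a-b) be a participant's concentration at day b divided by that at day a. Then

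FC(14-42) = FC(0-42) / FC(0-14).

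The same relation holds for the Group 1 / Group 2 ratio of geometric mean fold changes. Groups 1 and 2 have the same day-14 injections (IIV and placebo). If BCG does not alter the response to IIV, the IIV contribution cancels between them and only the BCG effect is left.

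**2. Group 1 against control, with assumed BCG effects.** Each day 14-42 value is the day 0-42 value divided by the day 0-14 value.

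| Assumed effect at day 14, then day 42 | Day 0-14 | Day 0-42 | Day 14-42 |
|---|---|---|---|
| 1.5-fold, then 1.5-fold | 1.50 | 1.50 | 1.50/1.50 = 1.00 |
| 1.5-fold, then 1.25-fold | 1.50 | 1.25 | 1.25/1.50 = 0.83 |
| 1.5-fold, then none | 1.50 | 1.00 | 1.00/1.50 = 0.67 |
| 2-fold, then 2-fold | 2.00 | 2.00 | 2.00/2.00 = 1.00 |
| 2-fold, then 1.41-fold (half on the log scale) | 2.00 | 1.41 | 1.41/2.00 = 0.71 |
| 2-fold, then none | 2.00 | 1.00 | 1.00/2.00 = 0.50 |

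Full persistence gives 1.00 on day 14-42 whatever the size of the effect. The day 0-14 column shows the early effect in every row. Only the day 0-42 column says whether an effect is present at day 42.

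**3. What this means for a test.** Assume a doubling that fully persists, 15 participants per group (section 13.0), two-sided alpha 0.05 (section 11.0), a t-test on the log fold change, and independent errors at each time point. From 4,000 simulated trials per setting, the proportions significant were:

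| Assumed log SD per time point | Day 0-14 | Day 0-42 | Day 14-42 |
|---|---|---|---|
| 0.35 | 97% | 96% | 5% |
| 0.50 | 74% | 74% | 5% |
| 0.70 | 47% | 46% | 5% |

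A normal-approximation check for day 0-42 gives 97%, 77% and 48%. The power depends on the assumed SD. The day 14-42 result does not: it stays at the alpha level because the true contrast is null.

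**4. The other BCG groups.** Section 13.0 places the day-14 antibody sample just before influenza vaccination. If the cytokine sample is likewise drawn before the day-14 injections, day 14 is a pre-BCG reference in Groups 3 and 4. In Group 4 it is already two weeks after IIV.

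**The case against.** Much of the case on the other side stands.

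- A reader might infer that a lasting BCG effect in Group 1 would disappear from the analysis altogether. It would not. Section 14.0 keeps the day 0-14 comparison, which measures induction against a pre-BCG sample. What is missing is the day-42 fold-change test.
- A reader might take a day 14-42 ratio below 1 as harm. It is a relative decline after an earlier rise, and the day 0-14 result beside it would show that rise.
- A reader might conclude that day 14 is the wrong reference throughout. For Groups 3 and 4 it is a sensible one, since BCG is given that day, and in Group 4 the day 0-42 interval also spans IIV. Nothing in the contradiction requires that contrast to be demoted.
- A reader might cite the stated outcome as fixing day 0. It says only when memory is assessed. The list of variables alone names the reference.
- Cytokine concentration is a separate listed variable at days 0, 14 and 42. If section 14.0 compares concentrations at each day, a lasting effect could show at day 42 there. The sentence may instead mean change in concentration, so this is unsettled. The point is therefore limited to the fold change.

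It could also be said that day 0-42 can be rebuilt from the two intervals. That works for a point estimate on the log scale. Section 14.0 specifies no log scale for the fold change, arithmetic mean fold changes do not multiply, and no interval or test would result.

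**Conclusion.** The point holds in limited form. The list of variables disagrees with section 14.0 and the Figure 3 symbols on the reference for day 42, and the day 0-42 fold change is defined but not analysed. In Group 1, early induction is tested, but presence of the effect at day 42 has no fold-change test. Under full persistence the day 14-42 ratio is 1.0 for any effect size. Under the assumed waning from 1.5-fold to 1.25-fold it is 0.83 while a 1.25-fold effect remains.

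The disagreement rests on the text alone. The ratios assume that the day-0 BCG does not alter the response to the day-14 IIV. If it did, day 14-42 would pick up that change, but it would still not measure the total effect at day 42. The effect sizes and SDs are illustrations.

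This is minor: a secondary outcome in a subset of 15 participants per group. The Part B primary antibody analysis is unaffected.

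**What to change.** 1. In section 14.0, keep day 0-14 and add the day 0-42 fold change against control for all groups, as the list of variables already defines it.
2. Add day 0-42 to the comparisons marked in Figure 3, and state the reference day for the plotted values.
3. Day 14-42 may stay if it is labelled: change after the day-14 injections, with a pre-BCG reference in Groups 3 and 4 (already post-IIV in Group 4), and persistence or waning in Group 1.

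The cost is SAP wording and one further contrast per treatment group for each cytokine and stimulus. No new blood is needed, because day-0 samples are already planned for the same participants.

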## **13.0 DESCRIPTION OF OUTCOMES AND VARIABLES**

### **Primary outcome**

Change in antibody levels to influenza virus strains included in the IIV, comparing levels at day 14 and day 42; just before and 4 weeks after influenza vaccination (for group 4, it will be 2 and 6 weeks after influenza vaccination).

We will use *Influvactetra* (Mylan ApS, Copenhagen), a quadrivalent inactivated influenza vaccine containing the following strains:

1. A/Victoria/2570/2019, IVR-215 (H1N1, pdm09-like strain)
2. A/Cambodia/e0826360/2020, IVR-224 (H3N2-strain)
3. B/Washington/02/2019, wild type
4. B/Phuket/3073/2013, wild type

Influenza antibodies are measured in hemagglutination-inhibition assay (HAI) yielding dilution titers with an expected range of <20 to 320 for this population. Geometric mean titers (GMT) will be determined by calculating the mean of the log-transformed duplicate titers followed by back transformation (calculated as  $10^x$ , where x is defined as the mean log-transformed titer).

Seroconversion is defined as a pre-vaccination HAI titer <10 and a post-vaccination titer  $\geq 40$ , or a pre-vaccination titer  $\geq 10$  and a minimum four-fold rise in post-vaccination titer.

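### Neither cytokine window tested in Part B isolates BCG for Group 4: day 0–14 contains no BCG, and day 14–42 estimates the BCG effect minus the influenza-vaccine effect

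*SAP*

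**What the plan says.** The schedule in Part B, section 10.0 (Trial design), gives Group 4 IIV on day 0, then placebo and BCG on day 14. Control (Group 2) gets placebo on day 0, then IIV and placebo on day 14.

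For trained immunity, section 13.0 states that "15 participants from each group will have extra blood samples taken on day 0, 14, and 42", and that the analysis will "determine whether BCG in the different combinations with influenza vaccine induces trained immunity in this population". The stimuli in the list of variables are "Poly(I:C), Pam3CSK4, LPS, and influenza vaccine at the various timepoints (day 0, 14, and 42".

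Section 14.0 (Immunological outcomes) plans that cytokine changes over day 0–14, and those "from day 14 to day 42 will be compared between the control group and the three treatment groups in linear regression analyses". Figure 3 marks between-group significance for the same two windows. The list of variables in section 13.0 differs: it expresses fold change relative to the day-0 value, at day 14 and at day 42.

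The SAP notices Group 4's offset elsewhere. For the antibody outcome it describes the day-14 and day-42 samples as "just before and 4 weeks after influenza vaccination (for group 4, it will be 2 and 6 weeks after influenza vaccination". It leaves Group 4 out of the B-lymphocyte analysis because its IIV is given at a different time. The cytokine analysis has no comparable provision.

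**The concern.** BCG after IIV is one of only three combinations under study. A contrast with control answers the trained-immunity question for that combination only if the two groups differ by BCG, and by little else, over the window compared. Over day 14–42 each group receives a different active vaccine. Group 4 also starts from a sample taken after IIV and control from one taken before it. An IIV response in control would be subtracted from any BCG response in Group 4. A true BCG effect could then be missed, or BCG could appear to lower cytokine production when it does nothing. Figure 3 would display either result as a between-group finding.

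**Working it through.** The SAP gives no power, SD or effect size for the cytokine analysis, so there is no stated figure to reproduce. The check has two parts.

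**1. Vaccine content of each window**

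Inputs: the schedule in section 10.0 and the sampling days in section 13.0. I assume that the day-14 cytokine sample, like the day-14 antibody sample, precedes that day's injections. Let b be the effect of BCG and i the effect of IIV on the change in response, taken as additive and lasting. Each cell is the vaccines received by the group in the window minus those received by control.

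| Window | Group 1 − control | Group 3 − control | Group 4 − control |
|---|---|---|---|
| Day 0–14 | b | 0 | i |
| Day 14–42 | 0 (IIV in both) | b | b − i |
| Day 0–42 | b | b | b |

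- Groups 1 and 3 each have one tested window that isolates BCG (day 0–14 and day 14–42 respectively). Group 4 has none.
- Over day 0–42 all three contrasts target b.
- At the day-42 sample, Group 4's IIV is 42 − 0 = 42 days old (6 weeks) and control's is 42 − 14 = 28 days old (4 weeks).

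**2. Illustration of size**

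Inputs: 15 per group (section 13.0) and two-sided alpha 0.05 (section 11.0). The effects, in SD of the change, are assumptions; the SAP offers nothing to anchor them.

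- Standard error of the day 14–42 contrast: √(2/15) = 0.365 SD.
- Expected contrast: d = b − i.
- Probability of a significant result in the direction of d, normal approximation: Φ(|d|/0.365 − 1.96).

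No BCG effect (b = 0), probability of a significantly negative contrast:
- i = 0.5: 0.5/0.365 = 1.37; Φ(−0.59) = 28%.
- i = 0.8: 0.8/0.365 = 2.19; Φ(0.23) = 59%.

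BCG effect of 0.8 SD, probability of a significant result in favour of BCG:
- i = 0: d = 0.8; Φ(2.19 − 1.96) = 59%.
- i = 0.5: d = 0.3; Φ(0.82 − 1.96) = 13%.
- i = 0.8: d = 0; Φ(−1.96) = 2.5%.

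These count one direction only. When d = 0 the two-sided rejection probability is 5%, half of it in each direction.

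**The case against.** **The better window is already in the SAP.** The list of variables refers fold change to day 0 and says it is compared between the randomization groups. This stands, and it narrows the point. The SAP does not lack a suitable measure; its analysis text and Figure 3 test a different one.

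**The information is not lost.** For mean change in concentration, the Group 4 contrast over day 0–14 plus that over day 14–42 equals the contrast over day 0–42. Figure 3 shows all three days for every group, so a reader could see an IIV response in control. This also stands and lowers the stakes, but it does not supply a prespecified test of BCG after IIV.

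**Stronger readings go too far.** A reader might infer that Group 4's second window shows BCG alone, or that the contrast can never show a BCG effect. The schedule contradicts the first, since Group 4 had IIV 14 days earlier. The second fails because b − i equals b when IIV does not change the read-out. Only one of the four stimuli is influenza vaccine, and the SAP gives no basis for assuming an IIV effect on responses to Poly(I:C), Pam3CSK4 or LPS. It does not say that there is none either.

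**The remedy is partial.** The 6-versus-4-week difference over day 0–42 matters most for the influenza stimulus, where an IIV response is most plausible. That stands and should be stated in the SAP.

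**Conclusion.** The point holds for Group 4 in the cytokine analysis. Tested as section 14.0 is written, this group gets no unconfounded test of BCG after IIV, although section 13.0 promises an answer for each combination. That Group 4's day 14–42 contrast estimates b − i follows from the schedule and needs no assumed effect size. How much it distorts the result depends on the IIV effect: nothing if that is zero, and substantial if it reaches 0.5–0.8 SD (28–59% probability of a significantly negative contrast with no BCG effect). Those figures rest on assumed effects, additivity and a normal approximation.

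A reader might extend the criticism to the other groups or to the main results. The documents do not support that. Group 3 against control over day 14–42 is a clean BCG contrast, because both receive IIV on day 14. The antibody and self-reported infection outcomes do not use these cytokine contrasts. This is a secondary, subset analysis: worth correcting, but with no bearing on the trial's primary conclusion.

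**What to change.** Reconcile the list of variables in section 13.0, the immunological analysis text in section 14.0 and Figure 3:

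- Name the day 0–42 change as the tested Group 4 versus control contrast for trained immunity, in line with the day-0 reference already in the list of variables.
- Present Group 4's day 0–14 and day 14–42 changes descriptively and not as tests of BCG. Drop the between-group significance mark for them in Figure 3.
- State that at day 42 the time since IIV is 6 weeks in Group 4 and 4 weeks in control, and that this matters most for the influenza-vaccine stimulus.

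The cost is SAP wording only. Day-0 and day-42 samples are already planned for 15 participants in each group. The drawback is the two-week difference in time since IIV, which a choice of window cannot remove with these sampling days.

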#### Primary outcome:

Mean change in GMT in samples from day 14 and 42 will be compared between the control group and the three treatment groups in linear regression analyses with adjustment for baseline level of GMT, age group, and sex. In case residuals are not normally distributed, the analysis will be performed on log-10 transformed change in GMT instead. The proportion of participants who seroconvert will be compared in logistic regression analysis with adjustment for age group and sex.

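### In the 15-per-group cytokine subset, changes from day 0 are compared without adjusting for the participant's own day-0 stimulated value, which costs precision

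*SAP*

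**What the plan says.** The cytokine measurements come from a subset: "15 participants from each group will have extra blood samples taken on day 0, 14, and 42" (SAP Part B, section 13.0, Secondary outcomes). The list of variables in section 13.0 records the stimulated concentration at all three days and defines the derived outcome as "Fold change in cytokine concentration from baseline value (day 0) to day 14 and 42 after stimulation with various stimuli", with randomisation group as the exposure and no baseline covariate.

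Section 14.0 (Immunological outcomes) sets the analysis. The outcomes include "fold change in cytokine concentration after stimulation from day 0 to day 14 and from day 14 to day 42", and they "will be compared between the control group and the three treatment groups in linear regression analyses". The one optional covariate follows: "With and without adjustment for responses in the control condition". Section 13.0 shows what that covariate is, since it plans the same comparison "with and without adjustment for responses in control medium". It is therefore the unstimulated response and not the day-0 stimulated value. The general methods paragraph of section 14.0 adds stratification by sex and age group, which does not supply the missing covariate.

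The antibody analysis in the same section is treated differently: change in titre is analysed "with adjustment for baseline level of GMT, age group, and sex".

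**The concern.** A change from day 0 subtracts the whole day-0 value, and a fold change divides by it. Unless the day-0 and follow-up values are perfectly correlated, this removes more than the day-0 value predicts. Participants who start low by chance tend to show a large rise, and those who start high a small one. With only 15 per group, day-0 means will differ between arms by chance, and part of that difference reappears with opposite sign in the comparison of changes.

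These samples are the SAP's evidence on the trained-immunity part of hypothesis (b) in section 2.0 of Part B. With groups this small, precision that could be had from data already collected is worth having. The SAP applies baseline adjustment to titres but not here.

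**Working it through.** **Inputs from the SAP.** 15 per group in four groups, so 60 in the subset (section 13.0). Two-sided 5% level (section 11.0). Stimulated concentration measured at days 0, 14 and 42 (section 13.0). The SAP states no power or precision figure for this subset, so there is none to reproduce.

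**Assumptions.** The SAP gives neither the SD nor the correlation r between day-0 and follow-up values. I take equal SDs at both days (SD = 1, on the analysis scale) and r = 0.3, 0.5, 0.7 and 0.8. Power is illustrated for a true difference of 0.8 SD between two arms.

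**Step 1: variance.** The change score has variance 2(1 − r). After adjustment for day 0 the residual variance is 1 − r². The ratio is (1 − r²) / [2(1 − r)] = (1 + r)/2. Estimating the covariate slope costs a factor of about 1 + 1/(60 − 4 − 2) = 1.019. The equivalent group size is 15 divided by the ratio that includes this cost.

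**Step 2: power.** Noncentral t, 15 against 15, residual df 60 − 4 = 56 unadjusted and 55 adjusted, with the slope cost included.

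| r | 2(1 − r) | 1 − r² | Ratio | Ratio with slope cost | Equivalent n per group | Power, unadjusted | Power, adjusted |
|---|---|---|---|---|---|---|---|
| 0.3 | 1.40 | 0.91 | 0.65 | 0.66 | 22.7 | 44% | 61% |
| 0.5 | 1.00 | 0.75 | 0.75 | 0.76 | 19.6 | 58% | 69% |
| 0.7 | 0.60 | 0.51 | 0.85 | 0.87 | 17.3 | 79% | 85% |
| 0.8 | 0.40 | 0.36 | 0.90 | 0.92 | 16.4 | 93% | 94% |

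**Step 3: chance imbalance.** The day-0 difference d between two arms of 15 has SE √(2/15) = 0.37 SD and a 95% limit of 1.96 × 0.365 = 0.72 SD. Given d, the unadjusted comparison of changes is shifted by −(1 − r)d. At the 95% limit the size of the shift is 0.50 SD (r = 0.3), 0.36 SD (0.5), 0.21 SD (0.7) or 0.14 SD (0.8). Adjustment removes it when the relation to day 0 is linear.

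**Step 4: simulation.** Four groups of 15, 4,000 runs per setting. Adjusted-to-unadjusted variance ratios for r = 0.3, 0.5, 0.7 and 0.8 were 0.66, 0.75, 0.88 and 0.92 for change. For fold change (lognormal, log-SD 0.6 assumed, log day-0 value as covariate) they were 0.73, 0.80, 0.88 and 0.94.

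**Step 5: the second interval.** Section 14.0 also compares the change from day 14 to day 42, where day 0 does not enter. If all three days are equally correlated, the covariance of that change with day 0 is zero and the covariate gains nothing. If correlation decays as r then r², the share explained is r²(1 − r)/2, which is 0.03 to 0.07 over the four values of r. The gains in Steps 1 to 4 therefore belong only to contrasts that start at day 0.

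**Step 6: which baseline.** In the vaccination schedule (section 10.0) group 1 receives BCG and group 4 receives influenza vaccine at day 0, so their day-14 sample is already post-vaccine. Only day 0 precedes active vaccination in all four groups. The two sections also disagree on the interval: the list of variables measures both fold changes from day 0, whereas section 14.0 and the Figure 3 legend use day 14 to day 42 for the second.

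**The case against.** The strongest reply is that change from baseline is a legitimate analysis. This stands. A reader might infer that the planned comparison is biased or produces too many false positives, but under randomisation it is unbiased on average and keeps its type I error. The cost is lost precision, plus imbalance conditional on the sample actually drawn.

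A second reply is that the gain is unknown because the correlation is unknown. This also stands: at 0.8 the gain is one to two percentage points of power.

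Third, the fix is not simply one more covariate. Modelling the day-42 level given day 0 answers a different question from the day 14 to 42 change. For group 3, which receives only placebo before day 14, the BCG effect lies wholly in that later window. This stands, and the change of estimand has to be stated.

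Fourth, the titre analysis is a weak precedent. Titres are measured in all participants only at days 14 and 42, so its baseline is post-BCG in group 1 and post-influenza vaccine in group 4. It shows that the SAP accepts baseline adjustment, but it is not a model to copy.

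A reader might also infer that the listed concentration scale, which begins at 0 pg/mL, makes fold change undefined in practice. The SAP does not say that stimulated day-0 values of zero occur. A log-scale model needs a rule for such values too, and fold change would remain in Figure 3. That argument does not carry the point.

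**Conclusion.** The point holds for comparisons that start at day 0 in the trained-immunity subset. Leaving out the day-0 stimulated value keeps the analysis valid on average but wastes precision, and it carries (1 − r) of any chance day-0 difference into the result. Adjustment would reduce the variance to about 65%, 75%, 85% or 90% of the change-score variance at assumed correlations of 0.3, 0.5, 0.7 or 0.8, slightly less after the cost of estimating the slope. These figures rest on equal SDs and on correlations that the SAP does not give.

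The reach is limited. It does not extend to the 300 Part B participants at large, since only 60 have these samples. It gives almost no gain for the day 14 to 42 change. It does not apply to the B-cell outcome, which is drawn on day 21 only. It concerns a secondary outcome that the SAP itself labels a subgroup analysis, so it is a worthwhile precision improvement and not a threat to the trial's main conclusions.

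**What to change.** In section 14.0 of Part B, for each cytokine and stimulus, regress the day-14 and the day-42 stimulated concentration on randomisation group, with the same participant's day-0 stimulated concentration as covariate. Put both on the log scale and state a substitution for values below the assay limit. Keep fold change as description in Figure 3.

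State that the day-42 model targets the day 0 to day 42 comparison already defined in the list of variables, and that it replaces the day 14 to 42 change as the main contrast because day 14 is post-vaccine in groups 1 and 4. If the day 14 to 42 change is kept, report it as supplementary. This also reconciles section 14.0 with the list of variables.

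The cost is one degree of freedom per model, a changed day-42 estimand that must be declared, and SAP wording. No new data are needed.
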